12.3 Appendix 3: Common Serious Adverse Events

The following list of serious adverse events are considered common for the study population defined in this protocol and should be reported by the investigator as described in Section 0. For IND safety reporting, single occurrences of the following events may be excluded from expedited reporting. If aggregate analysis of these events indicates they occur more frequently with study drug, an expedited IND safety report may be submitted to FDA.

- Anemia
- Anorexia
- Asthenia / Fatigue
- Back pain
- Bone pain
- Catheter related infection
- Dyspnea
- Haematuria
- Hydronephrosis
- Metastases to bone
- Metastases to central nervous system
- Nausea
- Obstructive uropathy
- Pain
- Prostate cancer metastatic
- Renal failure
- Renal failure acute
- Spinal compression fracture
- Spinal cord compression
- Urinary retention
- Urinary tract infection
- Urinary tract obstruction
- Vomiting

13 ATTACHMENT 1: SUBSTANTIAL AMENDMENT 4

I. The purpose of this amendment is:

Substantial Changes
1. Revise Study Design
DESCRIPTION OF CHANGE: Subjects who are continuing to derive clinical benefit from treatment with enzalutamide based on the investigator's medical opinion and have not met any of the discontinuation criteria as outlined in Section 3.4 of the protocol may be eligible to continue to receive treatment with enzalutamide in Study [REDACTED] upon approval of the protocol and activation of this study at the participating institution. Subjects who choose not to participate or are not eligible for Study [REDACTED] will complete their participation in Study 9785-CL-0121 by completing the safety follow-up visit upon activation of Study [REDACTED] at the institution.
RATIONALE: Astellas will close Study 9785-CL-0121 and allow subjects who are continuing to derive clinical benefit from treatment with enzalutamide to enroll in Study [REDACTED]. Study [REDACTED] allows investigators to follow their subjects per standard of care while still providing treatment with enzalutamide for their prostate cancer.

Nonsubstantial Changes
1. Update Sponsor contact information
DESCRIPTION OF CHANGE: Change of Astellas Medical Expert/Medical Monitor.
RATIONALE: Key sponsor personnel change.
2. Revise planned study period
DESCRIPTION OF CHANGE: Change planned study period to indicate an end date of first quarter 2017.
RATIONALE: The planned study period is updated to reflect the most current information.

II. Amendment Summary of Changes:

IV Synopsis, Design and Methodology and 2 Study Objective(s), Design and Endpoints

2.2.1 Study Design

WAS:

This is a multi-center phase 2 open-label extension study in subjects with prostate cancer who have completed MDV3100 treatment in a previous study with MDV3100 to assess the long-term safety of continued administration of MDV3100, when judged by the investigator to be in the best interest of the subject.

For the study duration, all subjects with castration-resistant prostate cancer (CRPC) will have to maintain androgen deprivation with an LHRH agonist/antagonist unless they underwent bilateral orchiectomy.

Subjects will be discontinued from study drug when continued administration of study drug is deemed to be not in the subject's best interest by the investigator based on clinical assessment.

Throughout the study, safety and tolerability will be assessed by the recording of adverse events, monitoring of vital signs and physical examinations, safety laboratory evaluations, and 12-lead electrocardiograms (ECGs).

Subjects will have a safety follow-up visit 30 days after their last dose of study drug.

IS AMENDED TO:

This is a multi-center phase 2 open-label extension study in subjects with prostate cancer who have completed MDV3100 treatment in a previous study with MDV3100 to assess the long-term safety of continued administration of MDV3100, when judged by the investigator to be in the best interest of the subject.

For the study duration, all subjects with castration-resistant prostate cancer (CRPC) will have to maintain androgen deprivation with an LHRH agonist/antagonist unless they underwent bilateral orchiectomy.

Subjects will be discontinued from study drug when continued administration of study drug is deemed to be not in the subject's best interest by the investigator based on clinical assessment.

Throughout the study, safety and tolerability will be assessed by the recording of adverse events, monitoring of vital signs and physical examinations, safety laboratory evaluations, and 12-lead electrocardiograms (ECGs).

~~Subjects will have a safety follow-up visit 30 days from their last dose of study drug.~~

Subjects that have not met any of the discontinuation criteria as outlined in Section 3.4 may be eligible to continue to receive treatment with enzalutamide in Study [REDACTED] upon approval and activation of this study at the participating institution. Subjects who enroll in Study [REDACTED] will not be required to have a safety follow-up visit.

Subjects who choose not to participate or are not eligible for Study [REDACTED] will complete their participation in Study 9785-CL-0121 by completing the safety follow-up visit upon activation of Study [REDACTED] at the institution.

IV Synopsis, Discontinuation Criteria

ADDED:

Astellas will be closing Study 9785-CL-0121. Subjects that have not met any of the discontinuation criteria as outlined in Section 3.4 may be eligible to continue to receive treatment with enzalutamide in Study [REDACTED] upon approval and activation of this study at the participating institution.

Subjects who choose not to participate or are not eligible for Study [REDACTED] will complete their participation in Study 9785-CL-0121 by completing the safety follow-up visit upon activation of Study [REDACTED] at the institution.

V Schedule of Assessments

Table 1: Schedule of Assessments

WAS:

Study Day	-32 to -1	1 ^a	29	85	every 12 weeks up to week 85	every 24 weeks from week 85	Safety FU
Week		1	5	13			30 days after last dose of MDV 3100
Window (days)		NA	± 3	± 7	± 7	± 7	± 7
Informed Consent	X ^b						
Inclusion/Exclusion Criteria		X					
Medical History		X					
Vital Signs ^c		X	X	X	X	X	X
Physical Examination		X	X	X	X	X	X
Weight		X	X	X	X	X	X
12-lead ECG		X	X	X	X	X	X
Clinical laboratory tests ^d		X	X	X	X	X	X
ECOG Performance Status		X	X	X	X	X	X
Adverse Events		X	X	X	X	X	X
Concomitant Medications		X	X	X	X	X	X
MDV3100 Dispensing		X	X	X	X	X	

- g. The final visit of the prior study with MDV3100 in which the subject is taking study drug and all assessments done during this visit, will serve as the initial visit (day 1) and visit assessments for this extension study.
- h. To ensure that MDV3100 is taken continuously without interruption, the subjects will be informed about the extension study at any of the visits during the previous study and sign ICF prior to visit on day 1 of this study.
- i. Vital signs (blood pressure, pulse rate, respiration rate, and temperature) will be obtained prior to study drug administration.

IS AMENDED TO:							
Study Day	-32 to -1	1 ^a	29	85	every 12 weeks up to week 85	every 24 ^d weeks from week 85	Safety FU ^e _f
Week		1	5	13			30 days after last dose of MDV 3100
Window (days)		NA	± 3	± 7	± 7	± 7	± 7
Informed Consent	X ^b						
Inclusion/Exclusion Criteria		X					
Medical History		X					
Vital Signs ^c		X	X	X	X	X	X
Physical Examination		X	X	X	X	X	X
Weight		X	X	X	X	X	X
12-lead ECG		X	X	X	X	X	X
Clinical laboratory tests ^d		X	X	X	X	X	X
ECOG Performance Status		X	X	X	X	X	X
Adverse Events		X	X	X	X	X	X
Concomitant Medications		X	X	X	X	X	X
MDV3100 Dispensing		X	X	X	X	X	

a) The final visit of the prior study with MDV3100 in which the subject is taking study drug and all assessments done during this visit, will serve as the initial visit (day 1) and visit assessments for this extension study.

b) To ensure that MDV3100 is taken continuously without interruption, the subjects will be informed about the extension study at any of the visits during the previous study and sign ICF prior to visit on day 1 of this study.

c) Vital signs (blood pressure, pulse rate, respiration rate, and temperature) will be obtained prior to study drug administration.

d) **If the subject is eligible to continue in extension Study [REDACTED], the final visit of Study 9785-CL-0121 will serve as the initial visit (day 1) for extension Study [REDACTED]. Subjects who enroll in Study [REDACTED] will not be required to have a safety follow-up visit.**

e) **If a new cytotoxic or investigational anticancer treatment is initiated before 30 days after last dose, then safety follow-up for Study 9785-CL-0121 should occur immediately before starting the new treatment.**

f) **Subjects who choose not to participate or are not eligible for Study [REDACTED] will complete their participation in Study 9785-CL-0121 by completing the safety follow-up visit upon activation of Study [REDACTED] at the institution.**

3 Study Population

3.4 Discontinuation Criteria for Individual Subjects

WAS:

Unless the subject withdraws consent, all subjects discontinuing study drug for any reason will have a safety follow-up visit 30 days after their last dose of MDV3100.

IS AMENDED TO:

Unless the subject withdraws consent, all subjects discontinuing study drug for any reason will have a safety follow-up visit 30 days after their last dose of MDV3100. **For subjects who enroll into Study [REDACTED], a safety follow-up visit is not required. For these subjects the final visit for Study 9785-CL-0121 will serve as Day 1 for Study [REDACTED] (± 7 days).**

5 Treatments and Evaluation

5.1.1 Dose/Dose Regimen and Administration Period

WAS:

In this study, subjects will continue to receive 160 mg/day of MDV3100 until the investigator feels that continued use of MDV3100 is not beneficial to the subject, or the subject withdraws consent.

Study drug should be taken as close to the same time each day as possible. Study drug can be taken with or without food. If dosing is missed on one day for any reason, double-dosing should not occur the following day.

IS AMENDED TO:

In this study, subjects will continue to receive 160 mg/day of MDV3100 until the investigator feels that continued use of MDV3100 is not beneficial to the subject, or the subject withdraws consent.

Since Astellas will close Study 9785-CL-0121, subjects that have not meet any of the discontinuation criteria as outlined in Section 3.4 may be eligible to continue receive treatment with enzalutamide in Study [REDACTED] upon approval and activation of this study at the participating institution.

Subjects who choose not to participate or are not eligible for Study [REDACTED] will complete their participation in Study 9785-CL-0121 by completing the safety follow-up visit upon activation of Study [REDACTED] at the institution.

Study drug should be taken as close to the same time each day as possible. Study drug can be taken with or without food. If dosing is missed on one day for any reason, double-dosing should not occur the following day.

5 Treatments and Evaluation

5.5.7 Follow-up of Adverse Events

WAS:

All adverse events occurring during the study are to be followed up until resolved or judged to be no longer clinically significant, or until they become chronic to the extent that they can be fully characterized (all follow-up results are to be reported to the sponsor or delegated CRO).

Since it is unpredictable how long such a follow-up will take, data from this follow-up generated after the subject's end of the study visit will be recorded by the investigator. Full details regarding this follow-up will be described in the study report, whenever necessary.

If during adverse event follow-up, the adverse event progresses to an "SAE" or if a subject experiences a new SAE, the investigator must immediately report the information to the sponsor.

Please refer to Appendix 2 (Liver Safety Monitoring and Assessment) for detailed instructions on DILI follow-up responsibilities related to history of symptoms, concomitant drug use, alcohol use, and recreational drug use.

IS AMENDED TO:

All adverse events occurring during ~~the study~~ **treatment** are to be followed up until resolved or judged to be no longer clinically significant, or until they become chronic to the extent that they can be fully characterized (all follow-up results are to be reported to the sponsor or delegated CRO).

~~Since it is unpredictable how long such a follow up will take, data from this follow up generated after the subject's end of the study visit will be recorded by the investigator. Full details regarding this follow up will be described in the study report, whenever necessary.~~

For those subjects that transition to Study [REDACTED], it is not needed to collect new AEs and SAEs after the last dose within this study, as these will be collected as part of the extension study.

~~If during adverse event follow up, the~~ **For subjects who do not transition to Study [REDACTED]** ~~any~~ **any** adverse event **that** progresses to an "SAE" or if a subject experiences a new SAE, the investigator must immediately report the information to the sponsor.

Please refer to Appendix 2 (Liver Safety Monitoring and Assessment) for detailed instructions on DILI follow-up responsibilities related to history of symptoms, concomitant drug use, alcohol use, and recreational drug use.

6 Discontinuation

6.1 Discontinuation of Individual Subject(s)

WAS:

A discontinuation is a subject who enrolled in the study and for whom study treatment is permanently discontinued prematurely for any reason.

The subject is free to withdraw from the study treatment and/or study for any reason and at any time without giving reason for doing so and without penalty or prejudice. The investigator is also free to terminate a subject's involvement in the study at any time if the subject's clinical condition warrants it.

If a subject is discontinued from the study with an ongoing adverse event or an unresolved laboratory result that is significantly outside of the reference range, the investigator will attempt to provide follow-up until the condition stabilizes or no longer is clinically significant.

IS AMENDED TO:

A discontinuation is a subject who enrolled in the study and for whom study treatment is terminated discontinued prematurely for any reason.

A safety follow-up visit will be performed approximately 30 days after the last dose of study drug, or prior to the initiation of another anti-neoplastic therapy, whichever occurs first.

For subjects who enroll into Study [REDACTED], a safety follow-up visit is not required. For these subjects, the final visit for Study 9785-CL-0121 will serve as Day 1 for Study [REDACTED] (± 7 days).

The subject is free to withdraw from the study treatment and/or study for any reason and at any time without giving reason for doing so and without penalty or prejudice. The investigator is also free to terminate a subject's involvement in the study at any time if the subject's clinical condition warrants it.

If a subject is discontinued from the study with an ongoing adverse event or an unresolved laboratory result that is significantly outside of the reference range, the investigator will attempt to provide follow-up until the condition stabilizes or no longer is clinically significant.

Subjects who choose not to participate or are not eligible for Study [REDACTED] will complete their participation in Study 9785-CL-0121 by completing the safety follow-up visit upon activation of Study [REDACTED] at the institution.

II Contact Details of Key Sponsor's Personnel

Astellas Medical Expert

WAS:

Astellas Medical Expert

[REDACTED], MD

Astellas Pharma Global Development-EU

Astellas Pharma Europe B.V.

The Netherlands

Telephone: [REDACTED]

Cell: [REDACTED]

Fax: [REDACTED]

IS AMENDED TO:

Astellas Medical Expert/Medical Monitor:

ECOG	Eastern Cooperative Oncology Group
e.g.	Exempli Gratia (for example)
ESV	End of Study Visit
EudraCT	European Union Drug Regulating Authorities Clinical Trials
ICF	Informed Consent Form
ISN	International Study Number
LLOQ	Lower Limit of Quantification
MDV3100	Study Drug
MedDRA	Medical Dictionary for Regulatory Activities
mg	Milligram
MRI	Magnetic Resonance Imaging
NCI-CTCAE	National Cancer Institute's Common Terminology Criteria for Adverse Events
PK	Pharmacokinetic
PSA	Prostate-specific Antigen
PT	Preferred Term
s	Second
SAF	Safety Analysis Set
SAP	Statistical Analysis Plan
SD	Standard Deviation
SOC	System Organ Class
TEAE	Treatment Emergent Adverse Event
WHO-DRL	World Health Organization Drug Reference list

1 INTRODUCTION

This Statistical Analysis Plan (SAP) contains a more technical and detailed elaboration of the principal features of the analysis described in the protocol, and includes detailed procedures for executing the statistical analysis of the primary and secondary variables and other data. The SAP is finalized and signed prior to hard lock of the database.

2 VISIT SCHEDULE

Table 1 Schedule of Assessments

Study Day	-32 to -1	1 ^a	29	85	every 12 weeks up to week 85	every 24 weeks from week 85	Safety FU
Week		1	5	13			30 days after last dose of MDV 3100
Window (days)		NA	± 3	± 7	± 7	± 7	± 7
Informed Consent	X ^b						
Inclusion/Exclusion Criteria		X					
Medical History		X					
Vital Signs ^c		X	X	X	X	X	X
Physical Examination		X	X	X	X	X	X
Weight		X	X	X	X	X	X
12-lead ECG		X	X	X	X	X	X
Clinical laboratory tests ^d		X	X	X	X	X	X
ECOG Performance Status		X	X	X	X	X	X
Adverse Events		X	X	X	X	X	X
Concomitant Medications		X	X	X	X	X	X
MDV3100 Dispensing		X	X	X	X	X	

- a. The final visit of the prior study with MDV3100 in which the subject is taking study drug and all assessments done during this visit, will serve as the initial visit (day 1) and visit assessments for this extension study.
- b. To ensure that MDV3100 is taken continuously without interruption, the subjects will be informed about the extension study at any of the visits during the previous study and sign ICF prior to visit on day 1 of this study.
- c. Vital signs (blood pressure, pulse rate, respiration rate, and temperature) will be obtained prior to study drug administration.
- d. Clinical laboratory tests, hematology and chemistry, will be obtained prior to study drug administration.

3 STUDY OBJECTIVE(S), DESIGN

3.1 Study Objectives

The main objective of this study is to follow up the long-term safety of continued administration of MDV3100 in prostate cancer subjects who were enrolled and completed MDV3100 treatment period in prior (e.g., phase 1) studies.

The long-term safety will be determined by:

- Adverse Events
- Vital Signs
- 12-lead ECGs
- Physical Examination
- Safety laboratory evaluation
- ECOG performance status.

3.2 Study Design

This is a multi-center phase 2, open-label extension study in prostate cancer subjects who have completed MDV3100 treatment in a prior study. In order to participate in this study, the subjects must have completed the prior study with MDV 3100, be in the state of at least stable disease and in the opinion of the investigator would derive benefit from continuing MDV3100 treatment. The final visit in the prior MDV3100 study, in which the subject is taking study drug, will serve as the initial visit for this extension study.

The extension protocol's baseline, for comparison purposes, will be a baseline from the prior MDV3100 study. In addition, all ongoing concomitant medications and AEs from the prior study will be transferred onto the appropriate case report forms (eCRFs) for this study.

All subjects will take 160 mg (4 capsules) MDV3100 once daily oral dose at the same time each day. MDV3100 can be taken with or without food.

Subjects will be discontinued from study drug when continued administration of study drug is deemed to be not in the subject's best interest by the investigator based on clinical assessments. Use of other investigational drugs will also lead to discontinuation.

Throughout the study, safety and tolerability will be assessed by the recording of AEs, monitoring of vital signs and physical examinations, safety laboratory evaluations, and 12-lead electrocardiograms (ECGs).

Subjects will have a safety follow-up visit 30 days after their last dose of study drug.

3.3 Assignment and Allocation

Subjects will be assigned to a subject number at study entry (signing of Informed Consent Form).

3.4 Transfer of data from prior study

Relevant data from the prior study has been transcribed to the eCRF of this study. This is done on the basis of specific instructions by the Investigators involved.

Demographic information (date of birth, ethnicity, race as described by the subject and height) collected at screening of the prior study with MDV3100 has been transcribed onto the appropriate eCRF for this study.

Medical history, as well as non prostate cancer medical history that stopped at or prior to screening, recorded at screening of the prior study with MDV3100 has been transcribed onto the appropriate eCRF for this study.

Medical history and disease history of the target disease recorded at screening of the prior study with MDV3100 has been transcribed onto the appropriate eCRF for this study.

As stated earlier, in addition, all ongoing concomitant medications (including non-medication therapies) and AEs from the prior study have been transferred onto the appropriate case report forms (eCRFs) for this study.

Further details can be found in the Investigators EDC Instruction Manual (see references).

Because of the transfer of all relevant data from the prior study, the reporting of the extension study will be exclusively based on the data available in the database of this extension study. The only exception is that for a number of safety assessments (Laboratory data, Vital signs, ECG data and the ECOG scale) as baseline the last assessment before the first MDV3100 intake of the prior study will be used.

4 SAMPLE SIZE

Subjects who were actively enrolled and have completed MDV3100 treatment in prior named studies, are eligible to participate in this study when continuation of MDV3100 is deemed by the investigator in the best interest of the subjects. There is no statistically determined sample size for this safety follow up study.

5 ANALYSIS SETS

In accordance with ICH recommendations in guidelines E3 and E9, the following analysis sets will be used for the analyses.

5.1 Safety Analysis Set (SAF)

Only one analysis set is defined for this study. The Safety Analysis Set (SAF) is defined as all subjects who have taken at least one dose of study drug in this extension study.

6 ANALYSIS VARIABLES

6.1 Efficacy Variables

Not applicable.

6.2 Safety Variables

Safety will be assessed by evaluation of the following variables:

- Treatment-emergent adverse events (TEAEs; frequency, seriousness, severity (NCI-CTCAE grade) and relationship to study drug)
- Safety laboratory variables (hematology and biochemistry)
- Vital signs (blood pressure, pulse rate, respiration rate, temperature and body weight)
- Physical examination
- 12-lead electrocardiogram (ECG)

TEAE: An adverse event observed after starting administration of study drug during the extension study. If a subject experiences an event during the prior study with MDV3100 which continues during this extension study, the event will be considered as TEAE only if it has worsened in severity (i.e. it is reported with a new start date during the extension period) All adverse events collected that begin within 30 days of taking the last dose of study drug will also be counted as TEAE.

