5.5 Adverse Events and Other Safety Aspects

5.5.1 Definition of Adverse Events (AEs)

An adverse event (AE) is defined as any untoward medical occurrence in a subject administered a study drug or has undergone study procedures and which does not necessarily have a causal relationship with this treatment. An AE can therefore be any unintended sign (including an abnormal laboratory finding), symptom, or disease temporally associated with the use of a medicinal (investigational) product, whether or not related to the medicinal (investigational) product.

An abnormality identified during a medical test (e.g., laboratory parameter, vital sign, ECG data, physical exam) should be defined as an AE only if the abnormality meets one of the following criteria:

- Induces clinical signs or symptoms
- Requires active intervention
- Requires interruption or discontinuation of study drug
- The abnormality or investigational value is clinically significant in the opinion of the investigator.

An AE observed after starting administration of the study drug is called a "treatment emergent adverse event" and usually summed up as the AEs in the clinical study report. If a diagnosis is made from the sign and/or symptom, the diagnosis should be recorded in preference to the listing of individual signs and symptoms. If not, the investigator should record each sign and symptom as an individual AE.

All AEs occurring after visit Day 1 should be recorded in the eCRF. All observed or spontaneously reported AEs will be recorded in the eCRF. Data to be recorded include a

description of the event, date and time of onset and end of the event, severity, action with respect to study drug, treatment required, relationship to study drug, and outcome of the event. All subjects who experience an AE will be followed up at appropriate time intervals until resolved or stabilized to the satisfaction of the investigator.

If an event recurs after it had resolved, it should be handled as a new AE. However, AEs that occur intermittently can be recorded as one AE. When the severity of an AE increases, the worst severity of that AE should be recorded for the entire duration.

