7.5.1 Adverse Events

AEs will be coded to system organ class and preferred term using the Medical Dictionary for Regulatory Authorities (MedDRA) and graded using NCI-CTCAE.

Treatment-emergent adverse events (TEAE) will be presented within each system organ class by preferred term, by relationship to study drug and by severity (NCI-CTCAE grade). AEs leading to dose reduction or temporary discontinuation of study drug, AEs leading to permanent discontinuation of study drug, SAEs, and SAEs by NCI-CTCAE grade will be summarized. AEs will also be summarized by NCI-CTCAE grade and relationship to study drug jointly.

All AEs data will be displayed in listings. In addition listings of deaths, SAEs, drug related AEs, AEs leading to dose reduction or temporary discontinuation of study drug and AEs leading to permanent discontinuation of study drug will be presented.

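### A prior-study AE that worsens in the extension can miss the TEAE tables: SAP 6.2 looks for a new start date that protocol 5.5.1 does not tell sites to create

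*SAP*

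**What the plan says.** SAP 6.2 gives the adverse event variable as "Treatment-emergent adverse events (TEAEs; frequency, seriousness, severity (NCI-CTCAE grade) and relationship to study drug"). An event that began in the prior study and continues into the extension is "considered as TEAE only if it has worsened in severity (i.e. it is reported with a new start date during the extension period").

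Protocol 5.5.1 governs how the site records a change in severity: "When the severity of an AE increases, the worst severity of that AE should be recorded for the entire duration". For a new record it gives one trigger: "If an event recurs after it had resolved, it should be handled as a new AE". It also lets intermittent events be kept as one AE.

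Protocol 2.2.1 and SAP 3.4 both have AEs still ongoing from the prior study carried onto this study's eCRF. SAP 3.4 limits reporting to the extension database. Its one exception is the pre-treatment baseline for laboratory data, vital signs, ECG and ECOG; AE grade is not included. For details of the transfer it refers to the Investigators EDC Instruction Manual.

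On the tables, SAP 7.5.1 says: "Treatment-emergent adverse events (TEAE) will be presented within each system organ class by preferred term, by relationship to study drug and by severity". Other summaries in the same section are not worded as TEAE: "AEs will also be summarized by NCI-CTCAE grade and relationship to study drug jointly", "SAEs, and SAEs by NCI-CTCAE grade will be summarized", and AEs leading to a dose reduction, a temporary stop or permanent discontinuation. All AEs are also listed.

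**The concern.** The SAP intends to count worsening of a carried-over event, but the only sign of worsening that it recognises is a new start date. A site that follows protocol 5.5.1 raises the grade on the existing record and leaves the start date in the prior study. The flag is then not set.

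Safety is the only endpoint, and the objective is the long-term safety of continued administration. Subjects enter on drug without a break, so some events will foreseeably be ongoing at Day 1. Their worsening on continued drug is something that an extension study should display. If the flag fails, the main incidence and severity tables omit those events, while other tables and the listings may show them. The report could then disagree with itself about the same event.

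**Working it through.** The plan has no figure to reproduce. The study is descriptive, with no calculated sample size, and the documents give no AE counts. The check is to apply the rules together.

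**Inputs**
1. Flag (SAP 6.2): the start date falls in the extension, or within 30 days of the last dose. A continuing event qualifies only through a new start date.
2. Record (protocol 5.5.1): worsening raises the grade on the same AE. Recurrence after resolution makes a new AE.
3. Scope (protocol 2.2.1, SAP 3.4): ongoing AEs enter this study's eCRF. Neither section exempts them from 5.5.1 or asks for a new record on worsening.
4. Comparison grade (SAP 3.4): no AE grade is brought over as a baseline, and raising the grade for the whole duration can overwrite the grade at transfer.

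**Trace.** The dates are illustrative: extension Day 1 on 15 June 2012, last dose on 10 January 2014.

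| Event | Start date on record | TEAE? |
|---|---|---|
| New AE in the extension | 1 Sept 2012 | Yes |
| Transferred, unchanged at grade 1 | 10 March 2012 | No |
| Transferred, grade 1 to 3, one record as in 5.5.1 | 10 March 2012 | **No** |
| Transferred, grade 1 to 3, re-entered on worsening | 1 Feb 2013 | Yes |

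Rows 2 and 3 have the same start date, so the flag cannot separate an unchanged event from one that rose by two grades. Row 4 shows that the flag works if the event is re-entered. The result therefore turns on the recording instruction, and the only one in the documents is 5.5.1.

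**Reach as worded.** SAP 7.5.1 attaches the TEAE label to the presentations by system organ class and preferred term, by relationship and by grade. The event in row 3 is absent from these. It remains in the listings and, where it qualifies, in the summaries worded as AEs or SAEs.

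**Partial dates.** SAP 7.9.1 moves an incomplete start date that would fall before the first dose of study drug to that dose date. It does not say which study's first dose is meant. If the extension's is meant, a transferred, unworsened AE dated only March 2012 would be moved to 15 June 2012 and would pass a pure start-date check. The worsening condition in SAP 6.2 should still exclude it.

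**The case against.** The best defence is that SAP 6.2 describes how worsening is entered on the eCRF, and that the EDC Instruction Manual tells sites to re-enter a worsened transferred AE. Protocol 5.5.1 does not mention transferred AEs, so it could be read as covering events within this study, with SAP 6.2 as the specific rule across studies. On that reading nothing is lost, and the trace above only restates the reading it assumes. This stands as a limit: the loss is conditional on an instruction that cannot be seen here. It does not remove the point, because neither the protocol nor the SAP states that division, and 5.5.1 points sites the other way.

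It is also fair that the more consequential worsening can still surface. An event that becomes serious, or leads to a dose change or discontinuation, falls under summaries that are not worded as TEAE.

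Two stronger readings are tempting. A reader might infer that worsened events drop out of every AE summary, because protocol 5.5.1 says treatment-emergent events are "usually summed up as the AEs in the clinical study report" and SAP 6.2 lists TEAEs as its AE variable. The documents do not support that: SAP 7.5.1 uses the TEAE label for some summaries and AEs or SAEs for others, and nowhere says that the second group is restricted. A reader might also infer that SAP 7.9.1 inflates the TEAE count with unworsened events. That needs the extension's first dose to be the one meant, and the imputed date to override the requirement in SAP 6.2 that the event has worsened. Neither is stated.

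**Conclusion.** The point holds in conditional form. Unless the EDC Instruction Manual requires re-entry on worsening, a transferred AE with a complete prior-study start date that worsens in the extension is omitted from the TEAE presentations by system organ class and preferred term, relationship and grade. The all-AE listings keep it and, as worded, so do the AE and SAE summaries.

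The number of affected subjects or events cannot be estimated, because the documents do not say how many AEs were ongoing at transfer or how many worsened. The conclusion assumes that sites follow 5.5.1 for transferred AEs as for any other. It should be fixed before hard lock, because the rule misclassifies events for the only endpoint and the repair is cheap. The partial-date wording needs a minor clarification only.

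**What to change.** Before database hard lock:

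1. **SAP 6.2.** Define a transferred AE as a TEAE if it has a new start date in the extension, or if its worst extension grade exceeds its grade at transfer (Day 1). Where the transferred grade was overwritten, use the prior-study grade and add it to the exceptions in SAP 3.4. If that grade is itself a worst grade, state that some worsening can still be missed.
2. **Fallback.** If no Day 1 grade can be recovered, tabulate all AEs ongoing at Day 1 by system organ class, preferred term and worst grade beside the TEAE table, labelled as an upper bound on worsened transferred events.
3. **Recording.** Reconcile protocol 5.5.1 and the eCRF instructions with the SAP rule. The sponsor is closing the study, so this helps only with data still to be collected.

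*Minor clarification, SAP 7.9.1.* Say which study's first dose is meant, and that the reset does not by itself make an original transferred record a TEAE. Keep the reset for AEs newly entered or re-entered in the extension. Without it, an event re-entered as June 2012 with the day unknown would be imputed to 1 June, before the 15 June Day 1 of the example, and could lose its flag.

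The cost is SAP wording and some programming, with no added patients or procedures. TEAE counts may rise. If the manual already requires re-entry, step 1 should change few or no counts.
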